5.2. Treatment Period

5.2.1. Treatment Period Part A

A treatment period will include assessments in 4 weekly visits including treatment with efgartigimod in eligible patients in need for (re-)treatment. A new treatment period can only be started if it can be completed within the 1-year duration of Part A of the trial (re-treatment in Part A can start at the latest on day 336). Otherwise, the patient can be transitioned to Part B after completing the EoA visit assessments (Table 1). These assessments should be completed

even if the patient is unwilling or unable to continue to Part B, then he/she should continue to the EoA visit.

The following assessments will be performed from visit 1 to visit 4 of each treatment period:

- Assessments of disease severity – the MG-ADL scale should be administered before the QMG scale*
- Suicidality assessment*
- Physical examination*
- Weight will only be measured in case there is an obvious weight change compared to the last weight assessment*
- Vital signs*
- ECG, only at visit 1 and visit 4 of each treatment period*
- Clinical laboratory tests. Patients need to have fasted at least 8 hours prior to sampling*
- Urinalysis*
- Urine pregnancy test (only for women of childbearing potential, see [DEFINITION OF TERMS](#))*
- Pharmacodynamic biomarkers (anti-AChR antibodies in AChR-Ab seropositive patients only, total IgG and subtypes [IgG1, IgG2, IgG3 and IgG4], and anti-MuSK antibodies in MuSK-Ab seropositive patients only)*
- ADA, only at visit 1 and visit 4 of each treatment period*
- Administration of efgartigimod as an IV infusion over a period of 1 hour. Patients will remain at the site for at least 1 hour following the end of the infusion for safety monitoring, based on the patient's clinical status
- Review of concomitant medication and rescue therapy
- Assess AEs, if any

*These assessments should be performed prior to administration of efgartigimod (predose).

At visit 1 of each subsequent treatment period, the conditions for (re-)treatment will be checked before administration of efgartigimod (see [Section 4.1](#)).

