5.2.2. Treatment Period Part B

A Treatment Period will include assessments in 4 weekly visits including treatment with efgartigimod in eligible patients in need for (re-)treatment. A new Treatment Period can only be started if it can be completed within the trial duration (up to maximum 3 years or until efgartigimod becomes commercially available or another option to access efgartigimod is available, whichever option comes first).

The following assessments will be performed from visit 1 to visit 4 of each Treatment Period:

- Assessments of disease severity (MG-ADL scale)*
- Weight will be measured at visit 1 and when there is an obvious weight change compared to the last weight assessment*
- Vital signs*
- ECG, only at visit 1 and visit 4 of each Treatment Period*
- Clinical laboratory tests (local labs), only at visit 1 and visit 4 of each Treatment Period.*
- Urinalysis, only at visit 1 and visit 4 of each Treatment Period*
- Urine pregnancy test (only for women of childbearing potential, see [DEFINITION OF TERMS](#)), only at visit 1 and visit 4 of each Treatment Period*
- ADA, only at visit 1 of each Treatment Period*
- Administration of efgartigimod as an IV infusion over a period of 1 hour. Patients will remain at the site for at least 1 hour following the end of the infusion for safety monitoring, based on the patient's clinical status
- Review of concomitant medication

- Assess AEs if any

*These assessments should be performed prior to administration of efgartigimod (predose).

At visit 1 of each Treatment Period, the conditions for (re-)treatment will be checked before administration of efgartigimod (see Section 4.1).

Patients may not receive (re-)treatment with efgartigimod if, at the time of (re-)treatment, they have clinical evidence of bacterial, viral or fungal disease, or any other significant disease which could confound the results of the trial or put patients at undue risk.

If a patient becomes eligible for (re-)treatment with efgartigimod but cannot complete the entire Treatment Period within duration of the trial, the patient should continue to the EoS visit.

If the investigator considers that the patient will not have a clinical benefit from re-treatment then the patient cannot start a new Treatment Period. The patient should then continue to the EoS visit.

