* An assessment on day 1 will be attributed to CnB in case it is before the infusion, to week 1 otherwise, except for MG-ADL and QMG (see section 2.2.2)

Baseline is defined in section 2.2.2.

For those patients who will start a new cycle, the last assessment in a cycle, prior to the infusion of the new cycle, will be allocated to the appropriate visit within the previous cycle and will also be allocated as the CB visit of the new cycle.

Per parameter and analysis window, the value closest to the target ADYP will be used in analysis tables and figures, other values will only be listed. If more than one value is located at the same distance from the target, then the latest in time will be selected.

	
Statistical Analysis Plan
	

ARGX-113-1705
	
Final Analysis
	
Final 1.0 of 20SEP2022

The value latest in time will be identified using, in order of preference, the assessment time, the visit label or the group identifier. Missing values are removed before the selection is made.

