4.3 ANTI-DRUG ANTIBODIES

4.3.1 Available data

During part A of the study, presence of anti-drug antibodies (ADA) to efgartigimod is measured at the roll-over visit, at baseline and week 3 of each cycle and at EoA.

During part B, ADA is measured at baseline and EoS only.

[figure not shown]
ADA samples are analysed in a 3-tiered approach:

- All samples are evaluated in the ADA screening assay and are scored ADA screening positive or negative.
- If a sample scored ADA screening positive, it is further evaluated in the confirmatory assay and is scored confirmed positive (positive immunodepletion) or confirmed negative (negative immunodepletion).
- If a sample is scored as confirmed positive, the samples are further characterized in the ADA titration assay (to determine titer) and are also further analysed in the Nab assay to confirm neutralizing activity (positive or negative).

If available, a titer result will be reported for the ADA confirmed positive samples. However, a titer result is not always available:

- In case the ADA confirmed positive sample could not be run in the titration assay (e.g. due to insufficient sample volume/quality to perform the titer analysis) the result will be described as ‘positive immuno-depletion’ and the sample should be considered as ADA positive.
- If a sample is negative in the titration assay, it will be reported as ‘negative titer’ but the sample should be considered as 'ADA positive' since it was confirmed positive in the second tier.
- If a sample is not reported or reported as ‘positive screen’, the ADA sample status is ADA unevaluable.

An overview of this 3-tiered approach and all possible ADA sample results that will be reported by the laboratory is given below. From these reported ADA sample results a final ADA sample status needs to be derived during the statistical analysis, as presented in the final column (Final ADA Outcome):

^a Missing screen includes the following terms (reported as reason not done): NA (not analysed), NR (no result), NS (no sample) and SL (sample lost). More details can be found in the IS data transfer agreement from SGS France to SGS SD office.

^b 'positive titer' is reported in case it was not possible to retrieve a numeric value.

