4.3.2 Derivation rules

4.3.2.1 SUBJECT CLASSIFICATION FOR ADA – OVERALL AND BY CYCLE

Table below gives an overview of how the ADA subject classification will be derived, starting from the patient baseline ADA sample status.

Subject ADA classification	Highest ^c post-baseline ^d sample status				
	ADA negative	ADA positive (missing titer ^a)	ADA positive (negative titer ^b or numeric titer value)		ADA not evaluable
Baseline ADA sample status					
ADA negative	ADA negative	Treatment Induced ADA	Treatment Induced ADA		ADA unevaluable
ADA positive (missing titer ^a)	Treatment Unaffected ADA	ADA unevaluable	ADA unevaluable		ADA unevaluable
ADA positive (negative titer ^b or numeric titer value)	Treatment Unaffected ADA	ADA unevaluable	titer < 4 x baseline titer: Treatment Unaffected ADA	titer ≥ 4x baseline titer: Treatment Boosted ADA ^e	ADA unevaluable
ADA not evaluable	ADA unevaluable	ADA unevaluable	ADA unevaluable		ADA unevaluable

^c Samples with missing titer have as reported ADA result 'positive immunodepletion' or 'positive titer';
^d Results reported as 'negative titer', i.e. titer value <1 will be set to value of 1;
^e Highest sample status, with order: (from low to high): ADA unevaluable, ADA negative, ADA positive (missing titer /positive immunodepletion), ADA positive with titer < 1 ('negative titer' as reported ADA result, titer value set to 1), ADA positive with titer ≥ 1 (i.e. positive titer and selecting the sample with highest titer)
^f For the overall ADA subject classification, the highest post baseline sample status over all cycles is used for comparison with the baseline ADA sample status.
 For the cycle ADA subject classification, the highest post baseline sample status within the cycle is used for comparison with the baseline ADA sample status.
^g Note: Four-fold difference in titer values is considered significant in case a twofold serial dilution is applied (=two times the dilution factor) (reference to Shankar et al., 2014).

ADA evaluable patient = patient classified as any of following categories: ADA negative, treatment unaffected ADA, treatment induced ADA, treatment boosted ADA.

ADA unevaluable patient = patient classified as unevaluable or with missing baseline ADA sample or without post-baseline ADA samples.

In case no ADA data is available at all, the participant cannot be classified.

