14.2.4.1	ADA: Number and Percentage of Patients with Anti-Drug Antibodies to Efgartigimod by Analysis Visit	SAF
14.2.4.2	ADA: Prevalence and Incidence of Anti-Drug Antibodies by Cycle and Overall	SAF
14.2.4.3	ADA: Descriptive Statistics of Anti-Drug Antibodies Titer Values by Overall ADA Subject Category	SAF
14.2.4.4	NAb: Number and Percentage of Patients with Positive NAb to Efgartigimod by Analysis Visit	SAF
14.2.4.5	NAb: Prevalence and Incidence of NAb by Cycle and Overall	SAF
14.2.4.6	NAb: Number and Percentage of NAb Positive Patients by Overall ADA Subject Category	SAF

SAFETY

ADVERSE EVENTS

14.3.1.1	Adverse Events Overview	SAF
14.3.1.2	Treatment-Emergent Adverse Events by MedDRA System Organ Class and Preferred Term	SAF
14.3.1.3	Serious Treatment-Emergent Adverse Events by MedDRA System Organ Class and Preferred Term	SAF
14.3.1.4	Non-serious Treatment-Emergent Adverse Events by MedDRA System Organ Class and Preferred Term	SAF
14.3.1.5	Grade 3 or More Treatment-Emergent Adverse Events by MedDRA System Organ Class and Preferred Term	SAF
14.3.1.6	Treatment-Related Treatment-Emergent Adverse Events by MedDRA System Organ Class and Preferred Term	SAF
14.3.1.7	Procedures-Related Treatment-Emergent Adverse Events by MedDRA System Organ Class and Preferred Term	SAF
14.3.1.8	Serious Treatment-Related Treatment-Emergent Adverse Events by MedDRA System Organ Class and Preferred Term	SAF
14.3.1.9	Treatment-Emergent Adverse Events Leading to Discontinuation of Study Drug by MedDRA System Organ Class and Preferred Term	SAF
14.3.1.10	Infusion-Related Reactions by MedDRA System Organ Class and Preferred Term	SAF
14.3.1.11	Serious Infusion-Related Reactions by MedDRA System Organ Class and Preferred Term	SAF

LABORATORY DATA

14.3.2.1	Descriptive Statistics of Laboratory Test Actual Values and Changes from Baseline	SAF
----------	---	-----

	Statistical Analysis Plan	
ARGX-113-1705	Final Analysis	Final 1.0 of 20SEP2022

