 - ^o Samples for anti-drug antibodies (ADAs) will be collected pre-dose on dosing days (if applicable) and will only be collected in the case of early discontinuation and not at the EoS visit.
 - ^p Efgartigimod will be administered as an intravenous (IV) infusion over a period of 1 hour at Visits 1, 2, 3, and 4 of each Treatment Period. Patients will remain at the site for at least 1 hour following the end of the infusion for safety monitoring based on the patient's clinical status. At TPE_nV₁, the conditions for (re-)treatment will be checked before administration of efgartigimod.
 - ^q All available vaccination history will be recorded as part of the participant's prior medication for vaccinations received in the past or concomitant medication for vaccinations received during the trial. For vaccines where multiple doses or boosters are received, only the most recent one must be recorded.
- * Assessments highlighted by use of bold italics indicate assessments that may be carried out as a telephone assessment visit under the conditions outlined in appendix 8 of the protocol.

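### By-cycle ADA and NAb status rests on two scheduled post-baseline samples in a re-treated Part A cycle but one or none in a Part B cycle, so a trend across cycles cannot be interpreted

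*SAP*

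**What the plan says.** **Sampling.** Protocol 5.2.1 schedules, for Part A, "ADA, only at visit 1 and visit 4 of each treatment period". SAP 4.3.1 agrees: after the roll-over visit, "at baseline and week 3 of each cycle and at EoA". For Part B, Protocol 5.2.2 has "ADA, only at visit 1 of each Treatment Period". Neither part takes ADA at the regular intertreatment visits.

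**End of Part B.** SAP 4.3.1 states: "During part B, ADA is measured at baseline and EoS only". The SAP's own Part B schedule (9.2.2, footnote o) says that ADA samples "will only be collected in the case of early discontinuation and not at the EoS visit". Protocol Table 2, footnote o, and Protocol 5.4 match the footnote.

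**Which cycle a sample belongs to.** Under SAP 2.2.1 a cycle runs until one minute before the first administration of the next cycle. SAP 2.2.4 adds that the last assessment before that infusion "will be allocated to the appropriate visit within the previous cycle and will also be allocated as the CB visit of the new cycle".

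**Classification.** By cycle, "the highest post baseline sample status within the cycle is used for comparison" with baseline (SAP 4.3.2.1; same rule for NAb in 4.3.2.2). A patient without a post-baseline sample is unevaluable. Incidence and prevalence both use evaluable patients as denominator.

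**Display.** Table 14.2.4.2 is "ADA: Prevalence and Incidence of Anti-Drug Antibodies by Cycle and Overall"; Table 14.2.4.5 is the NAb counterpart. SAP 2.4.3 does not separate Part B from Part A within a cycle number.

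**The concern.** A highest-of-several rule depends on how many samples there are. Here that number changes between the parts, and the cycle rows mix the parts in proportions that change with cycle number. Protocol 7.2.2 budgets blood volume for at most six treatment periods in Part A. With 21 days of dosing and a 30-day visit interval (51 days per cycle), seven starts fit by day 336, since 1 + 6 × 51 = 307. On that spacing, rows beyond the sixth or seventh cycle are Part B only, while the first rows are mostly Part A.

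Immunogenicity is the only tertiary objective covering both parts, and a by-cycle table invites reading as ADA by number of courses received. The sampling schedule can add to a trend in that table or mask one, and the planned rows do not let a reader tell which.

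**Working it through.** The plan states no ADA rate and no computed sample size (Protocol 8.1), so there is no figure to reproduce. The check counts the samples and then shows what the counts can do.

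**1. Scheduled post-baseline ADA samples per cycle**

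| Cycle | Week 3 | Exit sample | Next pre-dose | Total |
|---|---|---|---|---|
| Part A, re-treated in Part A | 1 | – | 1 | 2 |
| Started in Part A, open at EoA, re-treated in Part B | 1 | EoA | 1 | 2 or 3 (EoA may itself be the pre-dose sample) |
| Last cycle, started in Part A | 1 | EoA or ED | – | at least 1 |
| Part B, re-treated | 0 | – | 1 | 1 |
| Last cycle, Part B, early discontinuation | 0 | ED | – | 1 |
| Last cycle, Part B, reaches EoS | 0 | none by the schedules (1 by SAP 4.3.1) | – | 0 |

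Patients leaving Part B for ARGX-113-2002 complete the ED assessments, so they fall in the fifth row. The counts are the same whether by-cycle baseline means study baseline or cycle baseline; SAP 4.3.2.1 does not say which, and SAP 2.2.2 suggests the latter.

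**2. Same evaluable, baseline-negative patients: two samples against one**

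Let p be the positivity per sample and ρ the within-cycle correlation, both assumed. Then P(highest of two is positive) = 2p − [p² + ρp(1 − p)], and with one sample it is p.

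| p | ρ = 0 | ρ = 0.5 | ρ = 0.8 | ρ = 1 | One sample |
|---|---|---|---|---|---|
| 2% | 3.96% | 2.98% | 2.39% | 2.0% | 2% |
| 5% | 9.75% | 7.38% | 5.95% | 5.0% | 5% |
| 10% | 19.0% | 14.5% | 11.8% | 10.0% | 10% |
| 20% | 36.0% | 28.0% | 23.2% | 20.0% | 20% |

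Example: p = 0.10, ρ = 0.5 gives 0.20 − (0.01 + 0.045) = 0.145. If a share b of a pooled row has one sample, the row shows (1 − b) × 14.5% + b × 10%: 12.25% at b = 0.5 and 10% at b = 1.

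**3. Patients with no post-baseline sample**

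Take 100 patients, p = 10%, and half with a post-baseline sample. The SAP rate stays 10% on 50 evaluable patients. It would fall to 5% only if the others were counted as negative, which the SAP does not do.

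**4. Selection of who is evaluable**

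Assume 60% are re-treated and ρ = 0.8. In Part A the other 40% still have their week 3 sample (one sample is assumed here); in Part B only the re-treated are evaluable.

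| p, re-treated | p, others | Part A | Part B |
|---|---|---|---|
| 10% | 10% | 11.1% | 10.0% |
| 15% | 5% | 12.5% | 15.0% |
| 5% | 15% | 9.6% | 5.0% |

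Second row: two samples give 0.30 − (0.0225 + 0.102) = 0.1755, so Part A = 0.6 × 0.1755 + 0.4 × 0.05 = 0.1253. The sign of the difference changes with the assumption.

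**5. Prevalence**

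An evaluable patient positive at baseline counts as prevalent even if later samples are negative, and baseline is drawn in both parts. Suppose each sample detects existing ADA independently with probability q, and set missing-titer cases aside. Post-baseline detection falls from 1 − (1 − q)² to q; detection including baseline falls from 1 − (1 − q)³ to 1 − (1 − q)². For q = 0.5, 0.7 and 0.9 the relative falls are 33%, 23% and 9% against about 14%, 6% and 1%. Independence is the extreme case.

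**The case against.** A reader might infer that later cycles will show less ADA, and that a fall would come from the schedule alone. The documents do not support that. Fewer samples can only lower detected treatment-induced or treatment-boosted ADA, or leave it unchanged, among the same evaluable patients. The evaluable patients are not the same: those without a post-baseline sample drop out of the denominator, and late Part B rows rest on patients who were re-treated or left early. Step 4 shows Part B can come out higher. Nor can the Part B share of each cycle row be calculated, because the documents give no entry dates or cycle lengths.

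The plan also already shows much of the raw material. Table 14.2.4.1 gives sample status by analysis visit, so cycle-baseline and week 3 results appear separately. SAP 4.3.3 tabulates unevaluable patients by cycle, and all samples are listed (Listing 16.2.12.1). The endpoint is incidence and prevalence without a by-cycle trend, the analysis is descriptive, and the overall classification uses every cycle.

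These points stand and limit the weight of the concern. They do not remove it: sample status by visit is not the induced or boosted classification, the number of samples behind each by-cycle status is not shown, and SAP 6.1 records no caveat.

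**Conclusion.** The by-cycle rows of Tables 14.2.4.2 and 14.2.4.5 mix the highest of two samples with a single sample, on evaluable groups formed differently in the two parts. They cannot be compared across cycles, and neither a fall, a rise nor a flat line can be attributed to repeated dosing.

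The sampling-count effect ranges from nothing at ρ = 1 to a near doubling for independent samples (10% against 19.0% at p = 10%). Two samples from one patient within a cycle are unlikely to be independent, so the upper end is a ceiling. The selection effect has no fixed sign. Incidence is more exposed than prevalence. All rates here are assumptions, not trial data; the sample counts come from the documents. The overall rows do not carry this between-cycle comparison.

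**What to change.** Keep the classification rule and the overall rows. In SAP 4.3.3:

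- Present the by-cycle rows of Tables 14.2.4.2 and 14.2.4.5 separately by the part in which the cycle started, with evaluable N and the number of post-baseline samples per cycle.
- Add a supportive by-cycle incidence row from the next cycle's pre-dose sample only, the time point common to both parts. For the same patients this gives one sample in each part and no gap (10% against 10% in the example). Note on the table that it covers only re-treated patients.
- Reconcile SAP 4.3.1 with footnote o of SAP 9.2.2 on whether an ADA sample is taken at EoS.

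The pre-dose-only row should not replace the main by-cycle rows. It would make a patient's final Part A cycle unevaluable although a week 3 sample exists, and would extend the re-treatment selection to Part A.

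Cost: smaller cells, a short SAP edit and re-programming of two tables. No new samples are needed.

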3.3. Tertiary Endpoints

Part A only:

- Total MG-ADL score changes compared to the treatment period baseline of the first cycle (TP₁B) and the corresponding TP_nB in AChR-Ab seropositive patients.
- Total MG-ADL score changes compared to TP₁B and the corresponding TP_nB in the overall population (AChR-Ab seropositive and AChR-Ab seronegative patients).
- Total QMG score changes compared to TP₁B and the corresponding TP_nB in AChR-Ab seropositive patients.
- Total QMG score changes compared to TP₁B and the corresponding TP_nB in the overall population (AChR-Ab seropositive and AChR-Ab seronegative patients).
- Percentage decrease (compared to TP₁B and the corresponding TP_nB) of total IgG level and IgG subtypes in efgartigimod (re-)treated patients.
- Percentage decrease (compared to TP₁B and the corresponding TP_nB) of autoantibodies (anti-AChR antibodies and anti-MuSK antibodies) in efgartigimod (re-)treated patients.

Part A and B:

- Incidence and prevalence of anti-drug antibodies (ADA) to efgartigimod.

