ADA incidence = percentage of patients with treatment-induced or treatment-boosted ADAs (denominator: number of evaluable patients). Treatment-unaffected ADAs are not taken into account.

ADA prevalence = percentage of patients with treatment-unaffected ADA, treatment-induced ADA or treatment-boosted ADA (denominator: number of evaluable patients).

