4.3.2.2 SUBJECT CLASSIFICATION FOR NAb – OVERALL AND BY CYCLE

ADA confirmed positive samples were further evaluated in the NAb assay. All ADA negative samples were thus not analysed in the NAb assay but should be considered per default as NAb negative in the analysis.

If a NAb sample is not reported, the NAb sample status will be NAb unevaluable.

All samples evaluated in the NAb assay will be scored as NAb positive, NAb negative or NAb unevaluable by the laboratory. Based on these results, the patients will be categorized based on their baseline and post-baseline sample status as detailed in following table.

Subject NAb classification	Highest ^a post baseline ^b		
	NAb sample status		
	NAb negative	NAb positive	NAb not evaluable
Baseline NAb sample status			
NAb negative	baseline neg – post-baseline neg	baseline neg – post-baseline pos	NAb unevaluable
NAb positive	baseline pos - post-baseline neg	baseline pos – post-baseline pos	NAb unevaluable
NAb not evaluable	NAb unevaluable	NAb unevaluable	NAb unevaluable

^a Highest sample status in order: (from low to high): NAb unevaluable, NAb negative, NAb positive.

^b For the overall NAb subject classification, the highest post baseline sample status over all cycles is used for comparison with the baseline NAb sample status.

For the cycle NAb subject classification, the highest post baseline sample status within the cycle is used for comparison with the baseline NAb sample status.

NAb unevaluable patient = patient classified as NAb unevaluable or with missing baseline NAb sample or without post-baseline NAb samples

NAb incidence=percentage of patients with subject classification ‘baseline neg – post-baseline pos’ and ‘baseline pos – post-baseline pos’ (denominator: number of evaluable patients).

NAb prevalence=percentage of patients with subject classification ‘baseline neg – post-baseline pos’, ‘baseline pos – post-baseline pos’ or ‘baseline pos – post-baseline neg’. (denominator: number of evaluable patients).

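### ADA prevalence leaves out patients who are confirmed ADA positive both at baseline and after baseline when either titer is missing

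*SAP*

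**What the plan says.** Protocol 3.3 names the endpoint for Parts A and B: "Incidence and prevalence of anti-drug antibodies (ADA) to efgartigimod". The SAP builds it in three steps.

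- **Sample status (SAP 4.3.1).** Samples pass through screening, confirmation and titration. When a confirmed-positive sample cannot be titrated, it is reported without a titer, "and the sample should be considered as ADA positive".
- **Patient classification (SAP 4.3.2.1).** Baseline status is crossed with the highest post-baseline status. Missing titer is a sub-type of ADA positive: "Samples with missing titer have as reported ADA result 'positive immunodepletion' or 'positive titer". The evaluable set is defined by the outcome: "ADA evaluable patient = patient classified as any of following categories: ADA negative, treatment unaffected ADA, treatment induced ADA, treatment boosted ADA".
- **Prevalence (SAP 4.3.2.1).** "ADA prevalence = percentage of patients with treatment-unaffected ADA, treatment-induced ADA or treatment-boosted ADA (denominator: number of evaluable patients". Incidence uses the same evaluable set.

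SAP 4.3.3 reports incidence and prevalence by cycle and overall, in Table 14.2.4.2.

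**The concern.** Prevalence asks whether a patient has ADA at all. The SAP takes it from a classification designed for incidence, where a four-fold titer rise must be judged for patients already positive at baseline. If either titer is missing, the rise cannot be judged and the patient becomes unevaluable. That is right for incidence. For prevalence it discards a patient whose two samples the SAP itself calls ADA positive.

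Two patients show the effect. Both are positive without a titer at baseline. The first is negative afterwards, is classed as treatment-unaffected and is counted as prevalent. The second is still positive afterwards and is dropped. At stake is a named immunogenicity endpoint whose error, for these patients, can only run downward.

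**Working it through.** **Step 1. The table, cell by cell (SAP 4.3.2.1).** Rows are baseline status and columns are highest post-baseline status.

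| Baseline | Negative | Positive, no titer | Positive, titer | Not evaluable |
|---|---|---|---|---|
| Negative | negative | induced | induced | unevaluable |
| Positive, no titer | unaffected | **unevaluable** | **unevaluable** | unevaluable |
| Positive, titer | unaffected | **unevaluable** | unaffected or boosted | unevaluable |
| Not evaluable | unevaluable | unevaluable | unevaluable | unevaluable |

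The three bold cells have a confirmed-positive sample at both times. With both titers known, such a patient would be either unaffected or boosted. Both labels are in the prevalence numerator, so the missing titer cannot change the answer.

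**Step 2. A consistency check against the NAb tables.** Under SAP 4.3.2.2 only ADA confirmed-positive samples enter the NAb assay. A patient in a bold cell with valid, positive NAb results counts in NAb prevalence (Table 14.2.4.5) but not in ADA prevalence (Table 14.2.4.2). SAP 4.3.3 even plans a count of NAb-positive patients within the ADA-unevaluable category.

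**Step 3. Direction.** The plan states no ADA rate, so there is no figure to reproduce. Let P be the patients classified as prevalent, N the evaluable patients, and k the patients in the bold cells. The SAP reports P/N; with the bold cells restored it is (P+k)/(N+k). The difference is k(N−P)/[N(N+k)], which is positive whenever P < N and k ≥ 1.

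**Step 4. Size under assumptions.** The 167 is the maximum enrolment in SAP 1.3, and N+k = 167 assumes no other exclusions. P and k are assumed. Example: P = 16, N = 164, k = 3 gives 16/164 = 9.8% against 19/167 = 11.4%.

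| k | P/N near 5% | P/N near 10% | P/N near 20% |
|---|---|---|---|
| 1 | 8/166 = 4.8% → 5.4% | 17/166 = 10.2% → 10.8% | 33/166 = 19.9% → 20.4% |
| 3 | 8/164 = 4.9% → 6.6% | 16/164 = 9.8% → 11.4% | 33/164 = 20.1% → 21.6% |
| 10 | 8/157 = 5.1% → 10.8% | 16/157 = 10.2% → 15.6% | 31/157 = 19.7% → 24.6% |

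**Step 5. The same in terms of a missing-titer rate.** Assume 15% persistently positive from baseline, 8% treatment-induced, and a titer missing independently in a share m of positive samples. True prevalence is 23.0%. If a share u of the persistent positives is dropped, the SAP figure is [0.15(1−u) + 0.08]/(1 − 0.15u).

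| m | One post-baseline sample, u = 1−(1−m)² | Many post-baseline samples, u → m |
|---|---|---|
| 5% | 21.9% | 22.4% |
| 10% | 20.7% | 21.8% |
| 20% | 18.6% | 20.6% |

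The right-hand column is closer to the overall analysis. There the highest status over all cycles is used and a titered positive outranks an untitered one, so mainly a missing baseline titer matters.

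**The case against.** The best defence is that the point is small and visible. The endpoint is tertiary and descriptive (Protocol 3.3 and 8.4.2). SAP 4.3.3 tabulates unevaluable patients, baseline status and sample status by visit, and Listing 16.2.12.1 gives individual results. Missing titers may be rare. All this limits the importance of the point, but none of these displays gives a patient-level prevalence with the both-positive patients restored.

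A reader might infer more, in three ways.

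- **That every unevaluable cell holding a positive sample biases prevalence downward.** Ten of the 16 cells are unevaluable and seven of those hold a positive sample. Four of the seven, however, are excluded because the paired sample is not evaluable. That rule drops negatives with an unevaluable pair too, and "ADA unevaluable patient = patient classified as unevaluable or with missing baseline ADA sample or without post-baseline ADA samples" removes patients lacking a sample whatever the other one shows. The net direction is then not fixed. With 16 prevalent patients, 3 single-sample positives and 30 single-sample negatives among 167, the SAP rule gives 16/134 = 11.9%, and restoring all of them gives 19/167 = 11.4%.
- **That prevalence should count anyone with a positive sample, over those patients plus the patients classed ADA negative.** One positive sample would then suffice to be counted, while a negative would need two. Take 100 patients, 10 persistently positive, with 20% of post-baseline samples missing at random. The SAP rule gives 8/80 = 10.0%, which is correct; the alternative gives 10/(10+72) = 12.2%.
- **That NAb prevalence has the same fault.** It does not. SAP 4.3.2.2 uses no titer, and its exclusions are of the unevaluable-pair kind.

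Nor does a missing titer by itself remove a patient: two missing-titer cells, each paired with a negative sample, are kept and counted.

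**Conclusion.** The point holds for three cells: untitered positive followed by untitered positive, untitered positive followed by titered positive, and titered positive followed by untitered positive. For these patients the prevalence rule conflicts with the SAP's own sample-status rule, and ADA prevalence in Table 14.2.4.2 is too low whenever any occur. The direction is certain; the size is not. Over the assumed range in step 4 it is about 0.5 to 6 percentage points, with the upper end needing 10 such patients. Step 5 gives 0.6 to 2.4 points for the overall analysis under its assumed rates (23.0% less 22.4% to 20.6%). The documents do not support extending the claim of understatement to patients with an unevaluable or absent sample, or to NAb prevalence.

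**What to change.** Add one rule to SAP 4.3.2.1: for prevalence only, a patient whose baseline and highest post-baseline samples are both ADA positive counts as ADA positive in numerator and denominator, whether or not either titer is available. Apply it by cycle and overall, and print the number of patients it restores. Keep the titer-based evaluable set for incidence, where the ratio is needed, and show the two denominators separately because they may now differ.

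Leave the exclusion of patients with an unevaluable or absent baseline or post-baseline sample unchanged in the main figure. If a sensitivity analysis adds them back, it should add single-sample negatives as well as single-sample positives. NAb needs no change.

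The cost is a sentence, a small programming change on data already collected, and an entry in SAP 6.3. Reported prevalence will stay the same or rise.
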